5.2 Pre-Treatment Criteria

Prior to initiation of treatment on D1, participants' labs must re-meet eligibility. Participants must have organ and marrow function as defined by absolute neutrophil count $\geq 1,500/\text{mcL}$, AST(SGOT) and ALT(SGPT) $\leq 2.5 \times$ institutional upper limit of normal and creatinine clearance $\geq 25 \text{ mL/min}$ (as was used in the AMPLIFY trial).

5.3 Schedule and Description of Study Procedures (requirements also detailed in study calendar)

5.3.1 Screening and Pre-Enrollment Procedures (Day -7 to Day 1)

Patients with suspected heparin-induced thrombocytopenia will be screened to determine if they meet study eligibility criteria. Prior to initiation of any study procedures, a written IRB-approved informed consent will be obtained. Much of the information listed below will be obtained at the time of determining eligibility. Eligibility is verified after consent, and patients are enrolled only after eligibility is determined.

The window for baseline screening/assessment is up to 7 days prior to start of treatment.

Upon consent, the following study procedures will be performed:

- 5.3..1 Confirmatory Laboratory Test for the Diagnosis of HIT
- Heparin-PF4 EIA or accepted other confirmatory test (e.g. serotonin-release assay, platelet aggregation assay) is required if not already recorded in the 7 days prior to study treatment initiation.
 - If the patient's initial HIT confirmatory test is negative, but the patient presentation is highly suspect for HIT, perform a serotonin release assay.
 - Result may be pending at the time of enrollment.
- 5.3..2 Demographic and Medical History
- Date of birth, gender, race, hospital service.
 - Past medical history of significant medical/surgical disease and previous hospitalization.
 - History of thrombotic event(s).
 - History of HIT and/or previous exposure to heparin/LMWH.
 - Reason for initial hospitalization.
 - Reason for initiation of heparin/LMWH.
 - Type of heparin treatment, route of administration and length of therapy.
 - Previous use of other anticoagulation therapy
 - Concomitant medications.
- 5.3..3 Physical Examination, including:
- Height, weight. (Height documented within the month prior to D1 is acceptable)
 - ECOG

- Vital signs (temperature, pulse, respirations, blood pressure, oxygen saturation).
- Clinical assessment for signs and symptoms of thromboembolic complications and any significant findings.

5.3..4 Laboratory Tests

- Record pre-heparin CBC with platelet count and blood coagulation profile.
- Urine or serum HGC pregnancy test in women of childbearing age (acceptable if performed within 7 days prior to initiation of study drug regimen).
- CBC: hemoglobin, hematocrit, WBC with differential, and platelet count.
- Blood coagulation profile: Activated partial thromboplastin time (aPTT), prothrombin time/international normalized ratio (PT/INR).
- Serum Chemistries: creatinine, BUN, Na, K, CO₂ and glucose.
- Hepatic Profile: total bilirubin, AST, ALT.

5.3.2 **Imaging (Day -7 to Day +3)**

- As part of standard of care, all patients with confirmed HIT or high suspicion of HIT undergo bilateral lower extremity non invasive testing to rule out deep vein thrombosis. LENI is not required if the patient is diagnosed with a Pulmonary Embolism.
- This can occur anytime from Day -7 to Day +3. Only one test is required.

5.3.3 **Initiation of Therapy: Day 1**

Once the patient has been consented and is determined to meet inclusion/exclusion criteria as described above in Section 3.1 and 3.2, the following study procedures will be performed. These assessments do not need to be repeated if Screening was conducted on D1.

- Physical Exam
- Clinical Assessment for signs and symptoms of TEC and any significant findings
- Vital signs
- Weight
- ECOG
- Laboratory tests:
 - CBC: hemoglobin, hematocrit, WBC with differential, and platelet count
 - Chemistries: creatinine, BUN, Na, K, CO₂ and glucose
 - Hepatic panel: total bilirubin, AST, ALT
 - Coagulation profile: aPTT, PT/INR
- Record Concomitant Medications
- Assess and Record Adverse Events
- Initiation of Therapy: dispense study medication and diary
 - Administer study medication: Apixaban
 - Initiate daily oral therapy at 10 mg twice daily for 7 days followed by 5 mg twice daily thereafter.

5.3.4 **Hospital Course: Day 2 - Day of Discharge:**

The following procedures will be done on a daily basis until discharge from the hospital:

- Clinical Assessment for signs and symptoms of thromboembolic complications and any significant findings.
- Vital signs
- Laboratory Tests:
 - CBC: hemoglobin, hematocrit, WBC with differential, and platelet count
 - Chemistry Panel: creatinine, BUN, Na, K, CO2 and glucose
- Assess and record Adverse Events
- Record Concomitant Medications
- Record all doses of administered Apixaban (from the day it was initiated).

Before discharge, ensure enough study medication is dispensed to last at least until the 30 Day Follow Up visit (for HIT) or the 90 Day Follow Up visit (for HITT).

5.3.5 **Follow-up: Day 30 (+/- 5 days)**

The patient will be assessed on Day 30 (\pm 5 days) from initiation of therapy, preferably in clinic. If clinic follow up is feasible, all of the following data must be recorded. If patient is unable to come to clinic (ie due to living in another city or unable to travel), day 30 follow up can be completed by telephone interview and the labs, exam and vitals will not be recorded.

The following data must be recorded:

- Summary of patient's clinical course
- Any adverse events that occurred between Day of Discharge through Day 30 including signs and symptoms of TEC.
- CBC, chemistries, coagulation profile*
- Physical exam and vital signs*
- Concomitant Medications
- For patients discharged on apixaban:
 - Retrieve study medication and diary
 - Record the stop date of discontinuation of apixaban.

**unable to obtain if follow up is telephone interview*

5.3.6 **Follow-up for patients with HITT: Day 90 (+/- 5 days)**

The patient will be assessed on Day 90 (± 5 days), from initiation of therapy, preferably in clinic. If clinic follow up is feasible, all of the following data must be recorded. If patient is unable to come to clinic (ie due to living in another city or unable to travel), day 90 follow up can be completed by telephone interview and the labs, exam and vitals will not be recorded.

The following data must be recorded:

- Summary of patient's clinical course
- Any adverse events that occurred between Day of Discharge through Day 90 including signs and symptoms of TEC.
- CBC, chemistries, coagulation profile*
- Physical exam and vital signs*
- Concomitant Medications
- For patients discharged on apixaban:
 - Retrieve study medication and diary
 - Record the stop date of discontinuation of apixaban.

**unable to obtain if follow up is telephone interview*

5.3.7 **Follow-up 30 days after last dose of therapy (+/- 5 days)**

The patient will be assessed on 30 days (± 5 days), after last dose of therapy. If clinic follow up is feasible, all of the following data must be recorded. If patient is unable to come to clinic (ie due to living in another city or unable to travel), this follow up can be completed by telephone interview and the labs, exam and vitals will not be recorded.

The following data must be recorded:

- Summary of patient's clinical course
- Any adverse events through 30 days after the last dose of therapy including signs and symptoms of TEC.
- CBC, chemistries*
- Physical exam and vital signs*
- Concomitant Medications

**unable to obtain if follow up is telephone interview*

5.3.8 **Unscheduled Additional Visits**

For any unscheduled visits, between Day of Discharge and Day 30 for isolated HIT and Day 90 for HITT, that are related to HIT and require hospitalization and treatment, the following procedures should be performed if possible (ie will not be possible if patient is admitted to an outside hospital or over the weekend/evening and discharged before study team available)

- Clinical Assessment for signs and symptoms of thromboembolic complications and any significant findings.
- Physical exam
- Vitals
- Summary of patient's clinical course, including any imaging if performed
- Laboratory Tests:
 - CBC: hemoglobin, hematocrit, WBC with differential, and platelet count
 - Chemistries: creatinine, BUN, Na, K, CO2 and glucose
 - Hepatic panel: total bilirubin, AST, ALT
 - Blood coagulation profile: aPTT, PT/INR
- Assess and record Adverse Events
- Record Concomitant Medications
- Record all doses of apixaban.

5.3.9 Evaluation of Symptomatic Thromboembolic Complications (TEC).

Patients will be evaluated for thrombotic events at each visit. The diagnosis of symptomatic, venous or arterial thrombosis will be determined by the primary investigator and/or treating physician based on established clinical signs and symptoms and where indicated (as for VTE) by a confirmatory, objective diagnostic test per the accepted standard of care.

5.3.10 Treatment of Symptomatic Thromboembolic Complications (TEC).

Treatment of symptomatic TEC will be instituted by the primary investigator and/or treating physician per their standard of care. Patients who develop symptomatic TEC, which is the primary endpoint for this study, will be followed for safety throughout the study follow-up period.

5.4 **Agent Administration.**

Apixaban will be supplied by BMS.

5.4.1 Administration and Dosing.

Apixaban will be initiated at 10 mg twice a day orally for the first 7 days. After 7 days, the dose of apixaban will be changed to 5 mg twice daily. This dosing regimen is the FDA approved dose per package insert. Per FDA approved guidelines, there is no requirements for dose modifications once patients meets inclusion and exclusion criteria.

For patients who are unable to swallow whole tablets, 5 mg APIXABAN tablets may be crushed and suspended in water, 5% dextrose in water (D5W), or apple juice, or mixed with applesauce and promptly administered orally. Alternatively, APIXABAN tablets may be crushed and suspended in 60 mL of water or D5W and promptly delivered through a nasogastric tube. Crushed APIXABAN tablets are stable in water, D5W, apple juice, and applesauce for up to 4 hours.

No hydration or pre-medications are required prior to administration of apixaban. There are no dietary restrictions when taking apixaban. There are no specific precautions necessary when administering apixaban.

5.4.2 Dosage Forms and Strengths

- 5 mg, pink, oval-shaped, biconvex, film-coated tablets with “894” debossed on one side and “5” on the other side.
- Drug may be dispensed per institutional standard, including repackaging.

5.4.3 Drug Diary

Patients will be requested to maintain a medication diary of each dose of medication. The medication diary will be returned to clinic staff at the end of the study (one month for HIT patients and 3 months for HITT patients).

5.4.4 Missed Dose or Vomited Dose

If a dose of APIXABAN is not taken at the scheduled time, the dose should be taken as soon as possible on the same day and twice-daily administration should be resumed. The dose should not be doubled to make up for a missed dose.

For vomited dose(s): If a single episode of vomiting, the dose should be taken at the next scheduled dose timings. If repeated vomiting and the patient is unable to retain any oral medications, the patient should contact his/her doctor immediately and he/she may need to be either temporarily discontinued from the study medication or permanently discontinued from the study drug. An alternative medication will be necessary if apixaban is stopped.

5.5 Other Modalities or Procedures

Once patients are diagnosed with HIT as part of standard of care or there is high suspicion of HIT, patients will undergo bilateral lower extremity non invasive ultrasound (LENI) to determine the presences of deep vein thromboses. If DVTs are identified, there will be no change in therapy. Presence of DVT will affect the length of anticoagulation. If patients have DVT, this would qualify as HITT and the patient will require 3 months of apixaban instead of 30 days as indicated for isolated HIT. If LENI is negative for DVT, but patient develops and is diagnosed with a clot elsewhere after heparin exposure, this would also qualify as HITT and will require 3 months of apixaban. The LENI is not required if the patient is diagnosed with a Pulmonary Embolism.

5.6 General Concomitant Medication and Supportive Care Guidelines

Because there is a potential for interaction of apixaban with other concomitantly administered drugs through the cytochrome P450 system or the p-glycoprotein system, the case report form must capture the concurrent use of all other drugs, over-the-counter medications, or alternative therapies. [Appendix C](#) presents guidelines for identifying medications/substances that could potentially interact with the study agent(s).

The following medications are **not** permitted in the protocol:

- Any other drug or biological agent with anticoagulation action.
- Any other drug that is known to interact negatively with the study drug.
- Investigational agents.
- Myelosuppressive chemotherapy.
- Treatment with aspirin at a dose of more than 162 mg daily.

5.7 Criteria for Taking a Participant Off Protocol Therapy

Duration of therapy will be one month for patients with isolated HIT and 3 months for patients with HITT. In the absence of treatment delays due to adverse event(s), treatment may continue for 1 month for isolated HIT and 3 months for HITT or until one of the following criteria applies:

- Patient had initial high clinical suspicion for HIT as defined in section 3.1.2 but testing with PF4 or other accepted confirmatory test (serotonin-release assay, platelet aggregation assay) returned negative.
- New symptomatic TEC
- Intercurrent illness that prevents further administration of treatment
- Major bleed (See Section 6)
- Patient becomes pregnant
- Unacceptable adverse event(s)

- Participant demonstrates an inability or unwillingness to comply with the oral medication regimen and/or documentation requirements
- Patient refuses to receive transfused blood products should this intervention become clinically indicated
- Participant decides to withdraw from the protocol therapy
- General or specific changes in the participant's condition render the participant unacceptable for further treatment in the judgment of the treating investigator. It is requested that premature discontinuation of a patient should be discussed immediately with the principal investigator, [name], [contact].

Participants will be removed from the protocol therapy when any of these criteria apply. The reason for removal from protocol therapy, and the date the participant was removed, must be documented in the case report form (CRF). Alternative care options will be discussed with the participant.

When a participant is removed from protocol therapy and/or is off of the study, the relevant Off-Treatment/Off-Study information will be updated in OnCore.

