3.1 Eligibility Criteria

3.1.1 Hospitalized patients at MGH and participating Dana Farber/Harvard Cancer Center (DF/HCC) sites.

3.1.2 Patient must have a 4 T score of ≥ 5 as calculated by the following criteria:

- **Thrombocytopenia**
 - Platelet count fall >50 percent and nadir $\geq 20,000$ /microL – 2 points
 - Platelet count fall 30 to 50 percent or nadir 10 to 19,000/microL – 1 points
 - Platelet count fall <30 percent or nadir $<10,000$ /microL – 0 points
- **Timing of platelet count fall**
 - Clear onset between days 5 and 10 or platelet count fall at ≤ 1 day if prior heparin exposure within the last 30 days – 2 points
 - Consistent with fall at 5 to 10 days but unclear (eg, missing platelet counts), onset after day 10, or fall ≤ 1 day with prior heparin exposure within 30 to 100 days – 1 point
 - Platelet count fall at <4 days without recent exposure – 0 points
- **Thrombosis or other sequelae**
 - Confirmed new thrombosis, skin necrosis, or acute systemic reaction after intravenous unfractionated heparin bolus – 2 points
 - Progressive or recurrent thrombosis, non-necrotizing (erythematous) skin lesions, or suspected thrombosis that has not been proven – 1 point
 - None – 0 points
- **Other causes for thrombocytopenia**
 - None apparent – 2 points
 - Possible – 1 point
 - Definite – 0 points

3.1.3 Patient must meet one of the following:

- Have a confirmed diagnosis of HIT by Heparin-PF4 EIA or other accepted confirmatory test (serotonin-release assay, platelet aggregation assay).
- Have a high clinical suspicion of HIT (either Heparin-PF4 result is pending, or Heparin-PF4 result is negative or not obtained but a confirmatory test is pending)

Testing for HIT at MGH and participating DF/HCC sites is extremely reliable. MGH and participating DF/HCC sites currently use an extensively validated PF4-H IgG-based ELISA for HIT which has 94% specificity with a negative predictive value of 99.7% and a sensitivity that is close to 95%.

- 3.1.4 Patients can be treated with a non-heparin anticoagulant (such as argatroban, bivalirudin, or fondaparinux) for up to 7 days prior to enrollment.
- 3.1.5 Age 18 years or older.
- 3.1.6 ECOG performance status ≤ 2
- 3.1.7 Participants must have organ and marrow function as defined below:
- absolute neutrophil count $\geq 1,500/\text{mcL}$
 - AST(SGOT) and ALT(SGPT) $\leq 2.5 \times$ institutional upper limit of normal
 - creatinine clearance $\geq 25 \text{ mL/min}$ as was used in the AMPLIFY trial¹⁶

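### Section 5.7 makes a negative PF4 a mandatory reason to stop apixaban, with no exception for a second assay that is pending or due under 3.1.3, 5.3.1 and calendar footnote 6 (minor)

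*Combined protocol and SAP*

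**What the plan says.** **Stopping rule (protocol 5.7, first bullet).** The bullet applies to a patient described as follows: "Patient had initial high clinical suspicion for HIT as defined in section 3.1.2". It is met when "testing with PF4 or other accepted confirmatory test (serotonin-release assay, platelet aggregation assay) returned negative". Section 5.7 then adds: "Participants will be removed from the protocol therapy when any of these criteria apply". It also says: "Alternative care options will be discussed with the participant".

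**Entry (3.1.3).** A patient qualifies by confirmation ("Have a confirmed diagnosis of HIT by Heparin-PF4 EIA or other accepted confirmatory test") or by high clinical suspicion, which is spelled out as "either Heparin-PF4 result is pending, or Heparin-PF4 result is negative or not obtained but a confirmatory test is pending".

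**Second test (5.3.1 and study calendar footnote 6).** Where the patient's "initial HIT confirmatory test is negative, but the patient presentation is highly suspect for HIT, perform a serotonin release assay". Footnote 6 gives the same instruction after a negative PF4 EIA. Section 5.3.1 allows the result to be outstanding at enrollment.

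**Analysis set (13.6.2).** The per-protocol set, used for the primary analysis, drops patients later ruled out by negative confirmatory testing.

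**The concern.** The assays in the 5.7 bullet are joined by 'or', and any single criterion forces removal. A negative PF4 alone therefore satisfies the rule, even while the plan still regards the patient as highly suspect and is waiting for an SRA. Section 3.1.3 treats that same state, PF4 negative with a second test pending, as a reason to be allowed to start apixaban.

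Section 2.3 says thromboembolic complications are most frequent early in the disease and that suspected HIT calls for immediate non-heparin anticoagulation. Followed literally, 5.7 withdraws the study anticoagulant in that period, and it describes no way to resume if the SRA is positive.

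The bullet also points to 3.1.2 for high clinical suspicion. Section 3.1.2 is the 4T score that every patient must meet; the suspicion route is set out in 3.1.3.

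**Working it through.** **1. The rules side by side**

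| Patient | 3.1.3 | 5.3.1 / footnote 6 | 5.7, read literally |
|---|---|---|---|
| PF4 negative before entry, SRA pending | may start | SRA under way | a confirmatory test is already negative, so the criterion could be met at entry |
| PF4 pending at entry, returns negative, still highly suspect | was eligible | SRA due | stop before the SRA result |
| PF4 negative, SRA negative | – | work-up complete | stop (no conflict) |
| PF4 negative, suspicion no longer high | – | no SRA ordered | stop (no conflict) |

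The first row can be reconciled if the bullet refers to the test still to return. The second row cannot be reconciled unless 'testing' means the whole work-up.

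**2. The plan's own figures (13.1)**

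49 × 0.90 = 44.1, so at least 44 confirmed patients. The exact 90% interval for 34/44 is 0.645 to 0.871, which matches the stated 65% to 87%. Neither figure depends on the 5.7 wording.

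**3. How many true HIT patients could be caught**

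Inputs: PF4 sensitivity about 95% and specificity 94% (3.1.3); 10% negative confirmatory tests, or 4.9 of 49 (13.1). The prevalence p of true HIT among patients entering with PF4 pending is not given, so it is an assumption.

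- P(PF4 negative) = 0.05p + 0.94(1 − p)
- P(HIT given PF4 negative) = 0.05p / P(PF4 negative)

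*(a) Hold negatives at the planned 4.9, all by this route.* The number entering with PF4 pending is then 4.9 / P(PF4 negative).

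| p | P(PF4 negative) | Entering with PF4 pending | P(HIT given negative) | True HIT among 4.9 |
|---|---|---|---|---|
| 0.30 | 0.673 | 7.3 | 0.022 | 0.11 |
| 0.50 | 0.495 | 9.9 | 0.051 | 0.25 |
| 0.70 | 0.317 | 15.5 | 0.110 | 0.54 |
| 0.944 | 0.100 | 49 | 0.472 | 2.3 |

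The last row is the prevalence at which all 49 could enter with PF4 pending and still give 10% negatives. Over p = 0.30 to 0.70, moving sensitivity between 94% and 96% widens 0.11–0.54 to 0.09–0.64. If only half of the 4.9 come by this route, the counts halve.

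*(b) Let all 49 enter with PF4 pending and drop the 10% figure.* False negatives = 49 × 0.05 × p = 0.5, 1.2 and 2.2 at p = 0.2, 0.5 and 0.9. PF4 negatives would then number 37.3, 24.3 and 6.8, all above the planned 4.9.

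These counts are ceilings on patients stopped early, because only those still highly suspect go on to an SRA.

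**The case against.** **The completed work-up was meant.** 'Testing' can be read as the whole work-up, and 'initial' suspicion as suspicion that the result has displaced. This is probably the intent. But the text does not say so, and a mandatory removal rule should not rely on staff inferring an exception.

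**The reflex SRA is a screening step.** Section 5.3.1 covers Day −7 to Day 1, and the calendar marks the confirmatory test only in the screening column. Applying the SRA instruction after treatment starts is therefore partly inference. It is a reasonable one, since results may be pending at enrollment, and 3.1.3 lets a patient begin apixaban while a second test is awaited.

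**Stopping on a negative PF4 may be deliberate.** Section 2.1 calls the EIA the accepted US standard, and 3.1.3 cites a 99.7% negative predictive value. As a clinical policy this is defensible, but it does not fit a plan that starts and tests PF4-negative patients. With 95% sensitivity and 94% specificity, 99.7% corresponds to a prevalence of about 5%. At 30%, 50% and 70% the value would be 97.8%, 94.9% and 89.0%. A reader might infer that 99.7% is an error. The documents do not support that: it can hold in a lower-prevalence tested population, and no design figure uses it.

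**Patients are left unprotected.** A reader might infer this and multiply the counts by the 52.8% 30-day VTE risk in 2.1; for 0.11 to 0.54 patients that gives 0.06 to 0.29 events. The calculation assumes 30 days without any anticoagulant. Section 5.7 requires alternative care to be discussed, and 5.4.4, although written about vomited doses, says another agent is needed when apixaban stops. The product is not an estimate of harm.

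**The primary analysis is compromised.** A reader might infer this too. Section 3.1.3 accepts a positive SRA as confirmation and 13.6.2 removes only patients who are ruled out, so a PF4-negative, SRA-positive patient stays in the primary set. Follow-up for 30 days after the last dose (5.8) still covers day 30.

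**Conclusion.** The conflict is real and minor. As written, 5.7 requires study drug to stop on a negative PF4 in a patient whom 3.1.3 would admit and for whom 5.3.1 and footnote 6 want an SRA. The wrong cross-reference adds to the ambiguity.

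The likely reach runs from well under one to about two true HIT patients of 49. That range rests on assumed prevalence, on an unstated number entering with PF4 pending, and on the 3.1.3 assay performance holding in this population. Alternative anticoagulation should limit harm. The sample size, the 34/44 success rule and the definition of the primary set all stand.

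**What to change.** Replace the first bullet of 5.7 with:

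> Patient entered on high clinical suspicion (section 3.1.3) whose confirmatory testing is complete and negative. A negative PF4 while an SRA or other functional assay is pending, or due under 5.3.1, is not by itself a reason to stop apixaban.

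This also corrects the reference from 3.1.2 to 3.1.3. No change to 13.6.2 is needed. The other 5.7 criteria, including investigator judgment, stay as they are.

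**Cost.** One bullet, and no new test or visit. The downside is extra apixaban until the SRA returns in patients who prove not to have HIT. Assume the SRA takes 3 to 7 days. With 4.9 negatives, 2.6 to 4.8 of them lack HIT (4.9 − 2.3 to 4.9 − 0.11), which gives about 8 to 34 patient-days (2.59 × 3 to 4.79 × 7). At the AMPLIFY rate of bleeding reactions in 7.7.1 (15.6% over a mean of 154 days), that is 0.01 to 0.03 reactions.

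Under scenario (b) at p = 0.2, with an SRA for every negative, 36.8 patients without HIT × 7 days = 258 patient-days, or about 0.26 reactions. AMPLIFY patients did not have HIT, so thrombocytopenic patients on 10 mg twice daily could bleed more.
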